**1.E. Preliminary Data: Phlebotomy for prediabetes and T2DM).** To demonstrate the benefits of reducing iron on glucose homeostasis, we recently completed a pilot study in which subjects (N=11, 9M and 2F, aged  $57.2 \pm 1.2$  yr, BMI  $30.6 \pm 2$  kg/m^2) with prediabetes (N=3) or early T2DM (N=8) were treated with phlebotomy in order to reduce serum ferritin concentrations. No subjects had evidence of systemic inflammation as assessed by medical history or elevated C-reactive protein. Individuals treated with phlebotomy achieved a significantly lower serum ferritin level with biweekly to monthly 1 Unit donations (average  $3.4 \pm 0.5$  Units, or  $\sim 1.7$  L) of blood, providing further evidence that the elevations in ferritin were related to iron and not inflammation. Women started with lower ferritin ( $92 \pm 2$  ng/mL) compared to men ( $219 \pm 32$  ng/mL,  $p < 0.04$ ) and thus achieved less absolute lowering of their ferritin ( $56 \pm 7$  ng/mL) than did the men ( $150 \pm 33$  ng/mL). Average weights increased slightly but not significantly in both groups over the course of the study (1.8 kg in treated, 3.1 kg in controls,  $p = \text{NS}$ ). Blood hemoglobin concentrations tended to decrease in the treated group ( $p = 0.10$ ); only one subject declined to below the normal range (by 0.1 g/dL, less than 1% below normal) and recovered to normal by the end of the study. There were no serious adverse events and no fainting.

**Improved glucose tolerance after phlebotomy.** Phlebotomy treatment resulted in significant lowering of

area under the glucose curve (AUCg) during a 120 min oral glucose tolerance test (average improvement  $1340 \pm 570$  [mg/dL]\*min,  $p < 0.05$  by paired t test). Non-treated controls increased their AUCg value by an average of  $1110 \pm 670$  (mg/dL)\*min, significantly different from the treated group (Fig. 3,  $p < 0.04$ ). The decrement in the AUCg after phlebotomy tended to be correlated with the starting AUCg value ( $r = 0.667$ ,  $p = 0.13$ ) and the starting ferritin value ( $r = 0.641$ ,  $p = 0.063$ ). AUCg values also trended to decrease more in those with prediabetes than diabetes ( $-10.3 \pm 2.2\%$  compared to  $-2.9 \pm 2.3\%$ ,  $p = 0.06$ ), suggesting that early intervention, perhaps before critical loss of beta cell mass, will prove to have the greater beneficial effect.

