**Disposition index determined by frequently sampled intravenous glucose tolerance test (FSIGTT) is improved by phlebotomy.** A subset of the subjects (1 control, 8 treated) underwent FSIGTT before and after iron reduction. The disposition index (DI), which is the product of the values for insulin sensitivity ( $S_i$ ) and acute insulin response to glucose (AIRg), serves as a better predictor of diabetes risk than either  $S_i$  or AIRg alone (34). Among the treated subjects, DI improved in seven of eight ( $P < 0.04$  for the entire group, by paired t test). The single control subject undergoing FSIGTT experienced a 72% worsening in DI over the study period. Among all of the subjects, the increase in DI (log transformed) was significantly correlated to the change in ferritin during the study (Fig. 4,  $p < 0.04$ ). The reasons for the improvement in DI varied. Every treated subject improved in terms either of insulin secretion (N=6 of 9, average increase in those 6 of 23.7%,  $p = \text{NS}$ ), insulin sensitivity (N=6 of 9, average increase in those 6 of 51.9%,  $p = \text{NS}$ ), or both (N=3 of 9).

In this small study sample, there was a hint that iron reduction to the very lower limit of normal was not optimally beneficial, and a recent epidemiologic study has suggested a possible optimal ferritin level in the range

of ~40-60 for men and ~30-50 for women, values that are in the 2nd lowest decile of normal.

[figure not shown]

Fig 5. (A) Liver TNF $\alpha$  mRNA, (B) serum ALT, and (C) liver collagen 1 $\alpha$  mRNA in mice fed the

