## METHODS AND MEASURES

**DESIGN:** We propose a randomized, placebo-controlled trial to determine if reducing tissue iron stores by phlebotomy (blood donation) will improve measures of glycemia in Type 2 Diabetes (T2DM) or prediabetes. Adult subjects (N=240 total) aged 40-75, half with prediabetes and half with early T2DM (controlled by diet or up to 2 nonhypoglycemic agents) with ferritin values in the upper half of normal will be randomized to receive real or sham phlebotomy (blood donation), performed in the same manner as at Red Cross donation centers. Glycemia will be assessed by HgbA1C (primary endpoint), fasting glucose, and continuous glucose monitoring (CGM) before and after treatment. Glycemic outcomes will be assessed 6 and 12 months after achieving the target ferritin. The primary endpoint for which this study aim is powered is a change in HgbA1C at 6 months. As secondary outcomes, we will determine if that improvement is stable over a year, and if there are changes associated with iron reduction in serum alanine transaminase (index of NASH), insulin sensitivity by homeostasis model assessment (HOMA-IR), weight, lipids, blood pressure, changes in the number of diabetes medications for participants with diabetes, and changes in glycemic status (normal, prediabetes or diabetes) for participants with prediabetes. We will also correlate the degree of change in glycemia with the starting ferritin levels and the overall change in ferritin to determine targets and thresholds for iron reduction.

There will be two optional sub studies that will be conducted only at Wake Forest Baptist Medical Center. One will look more closely at liver complications of diabetes and the other will explore whether improvements in glucose levels are due to more insulin production or improved insulin action.

Iron may also play a role in the progression of fatty liver to scarring and cirrhosis. Since 75% of people with diabetes have some degree of fatty liver, we would also like to study how your liver reacts to the lowering of iron.

This will require some additional test, namely an MRI and a liver Ultrasound (Fibroscan). There will be approximately 40 people recruited at Wake Forest Baptist Medical Center for the liver sub study.

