### **Subjects selection criteria**

Subjects will have type 2 diabetes mellitus, or prediabetes, defined by HgbA1C criteria.

- **Inclusion Criteria.** Ages 40-75; At least 3 months since diagnosis of prediabetes or diabetes; HgbA1C value within three months or at screening of 5.7-6.4% for those with prediabetes, undiagnosed on no medication HgbA1C 6.5-6.9 and 7-8.5% for those with diabetes (the upper limit of the latter to reduce the likelihood of major changes in glycemic intervention during the trial period, and the lower limit to allow some room for improvement); Serum ferritin levels within 1 year or at the time of screening in the upper half of the normal range (>50 ng/mL for women and >100 ng/mL for men). C-reactive protein levels up to 11.0. Subjects will be on stable lifestyle therapy and 0-2 antihyperglycemic agents that are non-hypoglycemic (i.e. no sulfonylureas, glinides or insulin) to limit the chances of hypoglycemia if, as hypothesized, participants become more insulin sensitive with iron reduction. Aim 2 – serum ALT> 1.5 times the upper limit of normal, or; liver stiffness of > 12.5 kPa by Fibroscan transient elastography.
- **Exclusion Criteria.** Documented current anemia, hemoglobin levels within 0.5 g/dL of the lower limit of normal (<12.5 g/dL for women and 13.5 g/dL for men), or recent blood loss; bleeding diatheses (coagulation abnormalities or treatment with anticoagulants); serious chronic infections or chronic inflammatory conditions that could elevate ferritin as an "acute phase reactant;" C-reactive protein greater than 10.0, the upper limit of normal, to further validate the lack of significant chronic inflammation; active cancer diagnosis (excluding skin cell cancers other than melanoma); renal insufficiency (eGFR<60 ml/min); history of orthostatic hypotension; heavy alcohol use (NIH criteria, for men greater than 4 drinks on any day or 14/week, for women >3 drinks on any day or > 7/ week); pregnancy or premenopausal women of childbearing age, unless unable to become pregnant because of oral contraceptive use, IUD, birth control implants, surgical loss of ovaries or uterus. Aim 2 – individuals meeting the additional inclusion criteria for aim 2 will be tested for anti-HAV IgM, HBs Ag, anti-HBc. IgM, anti HCV IgM and IgG. Subjects who prove positive for any of these viral serologies, except for HCV IgG will be excluded. The latter will be tested for HCV RNA by PRC, and if negative they will be eligible for enrollment

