- c. Visit 2 (7-14 days) (fasting) (~1 hr):** Report to the Clinical Research Unit (CRU) at University of North Carolina at Chapel Hill (UNC) or Wake Forest (WF) School of Medicine. Review Adverse Events (AE's). Measure outcome variables (weight, blood pressure; blood for, insulin, lipid panel, CMP (14), Ferritin) and the Ultrasound Fibroscan (WFBH site only). Subjects who complete Visit 2 will be compensated \$50 for their time.

*Randomization* (1:1) to control (sham phlebotomy) or phlebotomy groups with final target ferritin levels of 20-40 ng/ml for males and 20-40 for females. Phlebotomy will not be performed if hemoglobin is lower than 12.5 g/dL for women and 13.0 g/dL for men; in that case, subjects will undergo repeat hemoglobin measurement every 2 months. If the hemoglobin value increases above the threshold for phlebotomy at Visits 3 or 4, phlebotomy will be performed; otherwise, participants will have an “end of study” visit 1 at six months. If blood pressure declines by > 20 mm Hg systolic, or pulse increases by > 30 bpm upon standing, phlebotomy will not proceed.

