### **Outcome Measure(s)**

The primary endpoint will be an improvement in glycemia as assessed by HgbA1C at the first end of study visit, 6 months after phlebotomy. Acutely, HgbA1C will be lowered by blood donation, because that test measures the lifetime exposure of a red blood cell (RBC) to glucose; phlebotomy will result in new RBC synthesis and hence younger RBC, but that effect should disappear soon after the normal RBC lifespan of ~3.5 to 4 months, well before the first post-treatment assessment at 6 months.

A secondary endpoint will be HgbA1C at 12 months to probe longevity of the effect. Based on animal data, we expect that value to be further improved relative to 6 months, but we have no human data on which to support that hypothesis. We do not anticipate that the effect will decline over that time based on reaccumulation of iron. This is a slow process: In individuals with hemochromatosis, for example, iron overload and its adverse effects may not appear until the 5th or 6th decades. In fact, we even anticipate continued improvement as the high levels of tissue iron redistribute and re-equilibrate as processes triggered by decreasing iron proceed, such as autophagy of ferritin complexes, and unloading of macrophages in the face of low hepcidin (Fig. 1).

Fasting glucose will also be assessed at 6 and 12 months after phlebotomy, with secondary endpoints being an improvement at 6 and 12 months. CGM will also be performed using the Abbott Freestyle Libre Pro system for 7-14 days to enhance validation of HgbA1C measures; it allows determination of multiple fasting levels, daily average glucose and various indices of glucose excursions, e.g. postprandial maxima and areas under the curve.

Other secondary endpoints include improvement in insulin sensitivity (decreased HOMA-IR calculated from fasting glucose and insulin), discontinuation of oral antihyperglycemic agents because of improved HgbA1C, change in ALT, changes in weight or blood pressure, and conversion from prediabetes (HgbA1C criteria) to either diabetes or normal glucose tolerance. The secondary endpoints were chosen because they are inexpensive and frequently assessed as part of usual clinical care, and because of the literature suggesting that they are also improved by phlebotomy. Outcomes will also be analyzed using initial, final, and change in ferritin as a continuous variable to interrogate possible optimal thresholds and targets for therapy.

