### **Analytical Plan**

#### **Statistical Plan and Data Analysis.**

The primary analysis will be an analysis of covariance to compare the mean change in the primary endpoint for each aim (HgbA1C at 6 months after phlebotomy for Aim 1, serum ALT at 12 months after phlebotomy for Aim 2, and DI at 6 months after phlebotomy for Aim 3) between the iron depletion and control groups in the full cohort of patients after controlling for the baseline levels of those measurements. The baseline HgbA1C is included as a covariate to increase study power by accounting for regression to the mean between the two time points.

*Secondary Analyses.* The effects of iron depletion on secondary continuous outcomes will be evaluated using analysis of covariance with adjustment for the baseline level of the factor being analyzed as well as the baseline HgbA1C level. For example, we will determine the degree of response (e.g. change in average glucose by CGM) as a function of starting ferritin, ending ferritin, and change in ferritin for determination of dose-response relationships. Treatment effects on dichotomous outcomes (e.g., conversion of pre-diabetes to diabetes) will be evaluated by exact logistic regression, controlling again for the baseline level of the analyzed factor. Ordinal logistic regression will be applied to compare categorical variables with more than 2 ordered categories. In expanded models, interaction terms between the treatment assignment and baseline HgbA1C level will be added to evaluate if the treatment effect differs across the HgbA1C range, and, in particular, between the diabetic and pre-diabetic patients in the study.

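### The analyses of response against starting and change in ferritin omit sex, although the sex-specific entry limits confound both measures with sex, most sharply near 100 ng/mL

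*Combined protocol and SAP*

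**What the plan says.** The Design paragraph under Methods and Measures states: "We will also correlate the degree of change in glycemia with the starting ferritin levels". The Outcome Measure(s) section adds: "Outcomes will also be analyzed using initial, final, and change in ferritin as a continuous variable", the aim being to look for thresholds and targets for therapy. The Analytical Plan, under Secondary Analyses, describes response "as a function of starting ferritin, ending ferritin, and change in ferritin for determination of dose-response relationships".

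The covariates named there for secondary continuous outcomes are the baseline of the outcome and baseline HgbA1C. The only interaction named is treatment by baseline HgbA1C. Sex appears in the Sample Size and Statistical Power paragraphs as one example of a possible subgroup stratification, and is not tied to the ferritin analyses.

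Elsewhere the protocol treats ferritin as sex-specific:

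- The entry limits are ">50 ng/mL for women and >100 ng/mL for men".
- The pilot reports that "Women started with lower ferritin": 92 against 219 ng/mL at the start, with falls of 56 and 150 ng/mL.
- The background cites an optimal ferritin level of "40-60 for men and ~30-50 for women".

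The treatment target is 20-40 ng/mL in both sexes.

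**The concern.** Starting ferritin is the baseline measure meant to show who benefits from iron reduction, and the Objectives name target populations and iron thresholds among the trial's products. Because women enter at half the male limit, low starting ferritin in this trial largely means being a woman. Change in ferritin inherits the same pattern, since participants starting lower have less distance to the common target. A model with ferritin but no sex term can then credit ferritin with a response difference that belongs to sex, and a single ferritin threshold could be read as applying to both.

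**Working it through.** The plan gives no sample size, power or error rate for the ferritin analyses, so there is no stated figure to reproduce.

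**1. What the entry limits fix.** At a cut of 100 ng/mL on the qualifying value, the lower group contains no men. For participants ending within 20-40 ng/mL, the smallest possible falls are:

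- women: more than 50 - 40 = 10 ng/mL
- men: more than 100 - 40 = 60 ng/mL

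On-target falls of 60 ng/mL or less therefore occur only in women. The pilot falls (56 and 150 ng/mL) fit this. Ending ferritin has the same target in both sexes, so the argument does not carry over to it.

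**2. How much ferritin variation is sex.** Assumptions: log-normal ferritin truncated at the entry limits, with half the participants women. The recruitment pool gives 832 + 837 = 1669 women of 3350.

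| Setting | Raw ferritin variance due to sex | Log ferritin variance due to sex |
|---|---|---|
| Pilot means 92 and 219, log SD 0.6 | 33-34% | 51% |
| As above, female mean 110 | 25% | 37% |
| As above, female mean 130 | 17% | 25% |
| As above, female mean 150 | 9% | 15% |
| Untruncated medians 50 and 100, log SD 0.5-0.9, 30-60% women | 10-46% | 26-57% |

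In the first row about 35% of participants start at or below 100 ng/mL, all women. In the last row, the group above 100 ng/mL is 60-93% men. The female mean matters because the pilot had only two women.

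**3. False-positive rate of a pooled treatment-by-ferritin test.** Inputs: 240 participants less 20% dropout gives n = 192 (96 per arm). Assume no ferritin effect within sex, a treatment effect that differs by sex by d HgbA1C points, and residual SD s. With R² the share of ferritin variance due to sex and 0.5 the SD of a 50:50 sex indicator, the expected z is approximately

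z = d × √R² × 0.5 × √n / (2s), and the rejection rate is Φ(z - 1.96) + Φ(-z - 1.96).

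| Scale (R²) | d | s | z | Approximate rate |
|---|---|---|---|---|
| Raw (0.34) | 0.2 | 0.6 | 0.67 | 10% |
| Raw (0.34) | 0.3 | 0.4 | 1.51 | 33% |
| Log (0.51) | 0.2 | 0.6 | 0.82 | 13% |
| Log (0.51) | 0.3 | 0.4 | 1.86 | 46% |

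Simulations on these assumptions gave 8-33% (raw) and 12-45% (log). A separate set, using the untruncated medians of 50 and 100 and log SD 0.5-0.7, gave for log ferritin:

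| Sex difference in treatment effect (residual SDs) | Without sex terms | With sex and sex-by-treatment |
|---|---|---|
| 0 | 4.1-4.7% | 4.8-4.9% |
| 0.3 | 10.6-12.3% | 4.5-4.6% |
| 0.5 | 19.4-25.9% | 4.8-5.1% |

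**4. Correlation in the treated arm alone.** If the planned correlation of glycaemic change with starting ferritin is run only in treated participants, a purely prognostic sex difference is enough. With n = 96, z = d × √R² × 0.5 × √n / s. For d = 0.2 and s = 0.6 to 0.4 this gives z = 0.95 to 1.43 (raw, 16-30%) and z = 1.17 to 1.75 (log, 21-42%). Simulation gave 15-29% and 21-39%.

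**5. Cost in precision.** Adding the sex terms multiplies the variance of the ferritin-by-treatment slope by about 1/(1 - R²): 1/0.66 = 1.5 (raw) and 1/0.49 = 2.0 (log).

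**The case against.** A reader might infer that any threshold this trial finds is mainly a sex contrast, or that ferritin and sex cannot be separated at all. The documents do not support that. Both sexes are present above 100 ng/mL, and under most of the assumptions above more than half of the ferritin variance lies within sex.

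A reader might also infer that every participant starting at 51-100 ng/mL must be a woman. That is exact only for the qualifying value. Eligibility accepts "Serum ferritin levels within 1 year or at the time of screening in the upper half of the normal range", and the Visit 2 draw includes "blood for, insulin, lipid panel, CMP (14), Ferritin"; the plan does not say which value is the starting one. If it is Visit 2, about 4-13% of men could be at or below 100 ng/mL, assuming log SD 0.7 and within-person variation of 10-30%.

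Other points in the plan's favour also stand:

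- In the randomised comparison, the error needs a treatment effect that differs by sex. The documents report none, and 0.2-0.3 points is a third to a half of the whole expected effect of about 0.6.
- The plan specifies neither a treatment-by-ferritin term nor a treated-arm-only correlation. Pooling the sexes is inferred from its silence, and sex is listed as a possible subgroup.
- The analyses are secondary and exploratory.
- If iron itself drives a sex difference in response, removing between-sex variation discards some real ferritin information.

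These points limit the claim but do not remove it. The covariates are listed and sex is not among them, and an optional subgroup analysis does not adjust the ferritin models.

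**Conclusion.** The concern holds for starting ferritin and change in ferritin, not for ending ferritin. Both are substantially confounded with sex, most sharply near 100 ng/mL. The degree is uncertain: sex explains about 9-46% of raw and 15-57% of log ferritin variance across the assumptions tried.

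The consequence is conditional. Under an assumed sex difference in treatment effect of 0.2-0.3 HgbA1C points and a residual SD of 0.4-0.6, a pooled treatment-by-ferritin test is falsely significant in roughly 8-45% of trials. With no such difference, or with sex terms included, the rate is about 5%. In a treated-arm-only correlation, a prognostic sex difference suffices. The primary ANCOVA of HgbA1C is unaffected. This is a cheap improvement to secondary analyses.

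**What to change.** In the SAP:

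1. Define starting ferritin, for example as the Visit 2 value.
2. Include sex and sex-by-treatment in every analysis of response against starting ferritin or change in ferritin.
3. Show ferritin-response curves separately for men and women, each over that sex's observed range, and draw no threshold for men below the range observed in men.
4. Optionally, enter log ferritin centred within sex.

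Sex and ferritin are already collected, so only wording changes. The downside is precision: the variance of the ferritin-by-treatment slope rises about 1.5-2 times, which is the price of separating ferritin from sex. Sex terms do not turn change in ferritin, which is measured after randomisation, into a randomised comparison; that limitation remains and should be stated alongside the results.

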- **Sample Size.** In our pilot study of the effects of phlebotomy, we did not measure HgbA1C, but did perform glucose tolerance testing where the difference in area under the curve from pre- to post-treatment was  $1130 \pm 1970$  mg-min/dl. Assuming this average change would be maintained through the day, and converting this change to the relative change in HgbA1C, the change would be expected to be a decrease of ~0.6% (in A1C units, not a change of 0.6% magnitude). With the variance observed, this means a sample size of 32 patients in each group will provide 80% power to detect a difference between the beginning and final HgbA1C in either treatment group at  $p < 0.05$  when pre- and post-phlebotomy results are compared within subjects. This agrees with the published results from another group that did measure HgbA1C, wherein they achieved a significant change ( $p < 0.001$ ) with an N of 31, but a shorter observation period and much less reduction in ferritin. A larger sample size (60/group, 240 total in Aim 1, half diabetes and half prediabetes, with

120 each being randomized to control and phlebotomy) will be recruited to facilitate possible subgroup analysis (e.g. stratification by age, treatment, race, sex) and to allow an up to 20% dropout rate, which is significantly higher than the experience of previous similar studies at Wake Forest University, wherein the dropout rates were in the 12-15% range. (In our pilot study, there were no dropouts.) Thus, we will be theoretically powered to analyze each target ferritin group separately, although the initial analysis will pool the two treatment groups.

- **Multisite study.** This is a multisite study, coordinated by WFUHS, and equal numbers will be recruited at each site, 120 at WFUHS and 120 at UNC Chapel Hill. The Liver substudy will recruit 40 people and the Glucose Tolerance Mechanism substudy will recruit 48 people. The sub studies will be conducted only at Wake Forest Baptist Medical Center.

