### **Glucose Mechanisms Substudy Outcome Measures**

Our primary endpoint will be an improvement in the FSIGTT DI, which is the best predictor of diabetes of the many indices arising from MinMod analysis of FSIGTT data (41). Secondary analyses will be the indices that directly quantify the two hallmarks and principal pathogenic factors in T2DM, namely insulin secretory capacity (AIRg) and insulin sensitivity (Si). As in Aim 2, and as in the pilot study on which this Aim is modeled, we will pool the diabetes and prediabetes groups for the primary analysis. This study is powered for that group analysis based on our preliminary data, although we will subanalyze by subgroups and with ferritin, AIRg, and Si as continuous variables to determine if there is evidence for an optimal ferritin target.

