*Statistical Power.* In our pilot study of the effects of phlebotomy, we did not measure HgbA1C, but did perform glucose tolerance testing where the difference in area under the curve from pre- to post-treatment was  $1130 \pm 1970$  mg-min/dl. Assuming this average change would be maintained through the day, and converting this change to the relative change in HgbA1C, the change would be expected to be a decrease of  $\sim 0.6$ . With the variance observed, this means a sample size of 32 patients in each group will provide 80% power to detect a difference between the beginning and final HgbA1C in either treatment group at  $p < 0.05$  when pre- and post-phlebotomy results are compared within subjects. This agrees with the published results from another group using HgbA1C, wherein they achieved a significant change ( $p < 0.001$ ) with an N of 31, but a shorter observation period and much less reduction in ferritin (28). A larger sample size (60/group, diabetes and prediabetes, control and phlebotomy) will be recruited to facilitate possible subgroup analysis (e.g. stratification by age, treatment, race, sex) and to allow for dropout. (Previous studies requiring FSIGTT at WF, had dropout rates were in the 12-15% range; in our pilot study, there were none.) Thus, we will be theoretically powered to analyze each target ferritin group separately, although the initial analysis will pool the two treatment groups.

The N for the change in transaminase levels by the same criteria (Aim 2) is 13, and in DI (Aim 3) is 16. Because the natural history is for both glycemia and NAFLD/NASH to deteriorate over time, the comparison of the control group with the treated group should be even more robust.

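### The stated 80% power belongs to a within-arm before/after test, not to the between-arm ANCOVA that is primary for every aim, so the two substudies are not shown to be powered

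*Combined protocol and SAP*

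**What the plan says.** The Statistical Power paragraph of the Analytical Plan, largely repeated under Sample Size, takes a pilot change in glucose area under the curve of 1130 ± 1970, converts it to an HgbA1C fall of about 0.6, and states that 32 patients per group "will provide 80% power to detect a difference between the beginning and final HgbA1C in either treatment group", "when pre- and post-phlebotomy results are compared within subjects". For the other two aims it adds: "The N for the change in transaminase levels by the same criteria (Aim 2) is 13, and in DI (Aim 3) is 16". It then argues that, because untreated disease worsens, "the comparison of the control group with the treated group should be even more robust".

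The Statistical Plan makes the primary analysis of each aim an analysis of covariance "between the iron depletion and control groups in the full cohort of patients", adjusted for baseline. The endpoints are HgbA1C at 6 months, ALT at 12 months and disposition index (DI) at 6 months.

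On numbers, 240 people are randomized 1:1, and "The Liver substudy will recruit 40 people and the Glucose Tolerance Mechanism substudy will recruit 48 people". The glucose mechanism section says of its pooled primary analysis: "This study is powered for that group analysis based on our preliminary data". Sample Size also says that the trial is "theoretically powered to analyze each target ferritin group separately".

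**The concern.** A sample size for one arm's before/after change does not carry over to a difference between two arms. With n per arm and the same SD of change, the difference has twice the variance of one arm's mean change. An uncontrolled change also contains regression to the mean, which the randomized comparison removes. The plan itself cites regression to the mean as a reason for baseline adjustment, and one route into Aim 2 is a raised ALT.

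The consequence falls mainly on the substudies. Figures of 13 and 16, set beside 40 and 48 recruits, look like ample power for the primary comparison. A null between-arm result in either substudy could then be read as stronger evidence of no effect than it is.

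**Working it through.** **Inputs from the documents.** Change 1130, with 1970 taken as the SD of within-subject change; p < 0.05, with two-sided assumed because sidedness is not stated; 32 per group; N = 13 (ALT) and N = 16 (DI); 1:1 allocation, so about 20 and 24 per arm in the substudies. Dropout of up to 20% is stated for the 240, and 12–15% is cited from earlier studies that used the intravenous glucose test.

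**Not in the documents.** Effect, SD or pre/post correlation for the between-arm contrast in any aim, the size of any control-arm change, and a dropout rate for the substudies.

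**1. The plan's own figure.** d = 1130/1970 = 0.574. The paired normal formula is n = ((1.96 + 0.84)/d)² ≈ 24; the noncentral t gives 26. At n = 32 the paired power is 88% (90% by the normal formula). So 32 is conservative for its own test but is not an 80% figure. Adding 20% dropout to 24–26 gives 30–33, but the text allots dropout to the larger 60 per group.

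**2. The same effect between arms, unchanged controls.** The noncentrality is d√(n/2) instead of d√n. By the two-sample t, 80% power needs 49 per arm, and 32 per arm gives 62%. The planned numbers are:
- Aim 1 pooled: 120 × 0.8 = 96 per arm, 98%.
- One disease group: 60 × 0.8 = 48 per arm, 79%.

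This assumes that the standardized effect survives the conversion from glucose AUC to HgbA1C.

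**3. Substudies.** Solving the paired t for 80% power gives d = 0.847 at N = 13 and d = 0.749 at N = 16. Between arms these need 23 and 29 per arm. For ANCOVA, the change-score SD is multiplied by √((1+r)/2), where r is the pre/post correlation and the two variances are assumed equal.

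| Assumption | Aim 2 (ALT) | Aim 3 (DI) |
|---|---|---|
| Unadjusted, 20 and 24 per arm (full retention) | 74% | 72% |
| Unadjusted, 17 and 21 per arm (about 12–15% dropout) | 67% | 66% |
| Unadjusted, 16 and 19 per arm (20% dropout) | 64% | 61% |
| ANCOVA, full retention, r = 0.5 | 85% | 84% |
| ANCOVA, full retention, r = 0.6 | 83% | 81% |
| ANCOVA, full retention, r = 0.7 | 81% | 79% |
| ANCOVA, 20% dropout, r = 0.3 | 82% | 80% |
| ANCOVA, 20% dropout, r = 0.5 | 76% | 74% |
| Controls worsen by 25% of treated change, full retention | 90% | 89% |
| Controls improve by 25% of treated change, full retention | 50% | 48% |

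After 20% dropout and without covariate gain, the detectable standardized difference at 80% is 1.024 (16 per arm) and 0.934 (19 per arm). Controls would have to worsen by 1.024/0.847 − 1 = 21% and 0.934/0.749 − 1 = 25% of the treated change.

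**4. If 13 and 16 share the margin hidden in 32.** Solved at 88%, they give between-arm power of 83% and 81% with full retention. Solved at 90%, they give 86% and 84%. After 20% dropout both versions fall below 80% unadjusted (71–77%).

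**5. The claim that the control comparison gains strength.** If controls worsen by a fraction k of the treated change, the noncentrality is d(1+k)√(n/2). It exceeds the within-arm d√n only when 1 + k > √2, that is, k > 0.41. In the pilot AUC data (section 1.E) controls rose by 1110 and treated subjects fell by 1340, so k = 1110/1340 = 0.83. For DI there is one control subject. The ALT series in Table 1 has no controls.

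**6. Groups named in the text.** Interventions and the Randomization paragraph define one active arm with one ferritin target, 20–40 ng/mL for both sexes. There are no separate target groups to analyze.

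**The case against.** The strongest reply is that the plan relies on controls getting worse, and the pilot supports this: a ratio of 0.83 is about double the 0.41 needed. That stands for the AUC measure, and the assumption is not baseless. But the pilot is small and its controls were untreated, not sham. The protocol also gives reasons why sham controls might improve: it acknowledges placebo effects, and overweight or obese participants are counselled on weight loss. For ALT and DI there is almost no control evidence.

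A second reply is that the main trial does not depend on the flawed figure. This stands. A reader might infer that Aim 1 is underpowered; on the plan's own standardized effect it is not.

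A third is that the substudy shortfall is conditional. This also stands. A reader might infer that the substudies definitely lack power, or that their power is 60–75%. The documents give no ALT or DI effect, SD or correlation, and the 20% dropout is stated only for the 240. Several plausible combinations reach 80%. The equal-variance ANCOVA formula is itself doubtful for ALT, whose SD falls from 46 to 19 in Table 1.

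Finally, a reader might infer that a within-arm change will be reported as the result. The Statistical Plan fixes the between-arm comparison as primary, so that is not what it says.

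**Conclusion.** The mismatch holds: the only stated power is for a test that is not the primary analysis of any aim, and the 32-for-80% figure does not follow from its inputs. For pooled Aim 1 the error has no practical effect, and for a single disease group power is close to 80%. For Aims 2 and 3 the supportable statement is that adequate power is not shown. With unchanged controls and no covariate gain it is 72–74% at full retention and 61–64% at 20% dropout, if 13 and 16 are two-sided 80% paired figures. Across the other assumptions examined it runs from about half to about 90%. The deciding inputs (correlation, control-arm change and substudy dropout) are not in the plan. The assertion that the controlled comparison is stronger needs control worsening above about 41% of the treated change, which is not established for ALT or DI.

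**What to change.** Replace the power text in both Sample Size and Statistical Power with between-arm ANCOVA power, or the detectable difference at 80%, at expected completers for each aim. State the assumed effect, SD, pre/post correlation, control-arm change, sidedness and dropout, and give a sensitivity range for correlation and control change. Do not enter a single back-solved power figure for Aims 2 and 3 as fact.

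In the same edit:
- correct the 32-for-80% statement;
- qualify or delete the sentence on greater robustness and the statement that the mechanism substudy is powered;
- delete the sentence on separate target ferritin groups and pooling of two treatment groups;
- state that within-arm tests are descriptive.

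The cost is protocol wording. Stated power for Aims 2 and 3 may become less favourable. No extra patients, visits or analyses are needed.
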